## Protocol

### 1. Project Title:

Comparison of obturator nerve blockade and neuromuscular blockade for the prevention of adductor spasm in patients undergoing transurethral resection of bladder tumors.

### 3. Abstract:

Transurethral resection of bladder tumor(s) (TURBT) is a commonly performed procedure to diagnose and treat bladder cancer. The obturator nerve is located lateral to the bladder wall in the pelvis prior to innervating the adductor muscles of the thigh. The adductor muscles include the adductor longus, adductor brevis, adductor magnus, and the pectineus muscle. These muscles are innervated by the obturator nerve and the adductor magnus muscle receives additional innervation from the tibial nerve [1]. In addition to hip adduction, these muscles contribute to flexion/extension as well as internal and external rotation of the hip [1].

Depending on the location of the tumor(s), electrocautery or surgical stimulation may result in stimulation of the obturator nerve, resulting in adduction of the leg, which is called the adductor reflex or spasm. This may occur violently and unexpectedly, and result in bladder perforation, bleeding, or cancer dissemination [2].

Ultrasound-guided obturator nerve blockade has been advocated as a technique to minimize or ablate the obturator reflex [2-4] in patients receiving spinal or general anesthesia for TURBT. Quadriceps weakness secondary to peripheral nerve blocks has been associated with an increased risk of falls in the orthopedic population [5-8]. Although obturator nerve blockade (ONB) results in adductor weakness [9, 10], it is not

known if this results in an increased fall risk. Much of the anesthesiology literature on ONB is focused on patients undergoing knee surgery and, to our knowledge, no literature exist regarding the incidence of falls in patients receiving an ONB for TURBT.

To date, there are no prospective studies comparing the incidence of adductor spasm in patients undergoing general anesthesia with neuromuscular blocking agents versus obturator block. No major complications—including falls—have been reported with obturator nerve blocks. This may be a reflection of underutilization, lack of reporting, or simply a reflection of their use primarily in an orthopedic patient population whose mobility status is limited and closely observed.

#### 4. Background:

Much of the available data on obturator blocks is taken from the orthopedic anesthesia literature on patients undergoing knee surgery. To date, there are no complications (including falls) related to obturator blocks reported in the literature. ONB is performed in patients undergoing TURBT to minimize or ablate the obturator reflex [2-4].

Ultrasound guided regional anesthetic techniques have a long record of safety and efficacy, and are commonly performed for patients undergoing surgery in both the outpatient and inpatient setting.

Neuromuscular blocking medications are commonly used to prevent patient movement under general anesthesia. Use of neuromuscular agents may result in postoperative weakness, which may lead to hypoxemia and airway obstruction, complaints of muscle weakness or fatigue, longer postanesthesia care unit stays, delays in tracheal extubation, increased risk of pulmonary aspiration, and atelectasis [11]. Additionally, adductor spasm has been reported despite the use of these medications [12, 13].

Furthermore, there is a study that suggests that use of an obturator nerve block in patients undergoing TURBT may prolong time to cancer recurrence in patients with superficial bladder tumors [14]. The obturator block results in a decreased incidence of adductor spasm, which allows for optimal surgical conditions and improved tumor resection [14]. The incidence of adductor spasm during TURBTs is currently unknown. While one study has estimated the incidence to be 16.5% [18], three others have reported it to be 40-55% [13, 19, 20] in patients with posterolateral bladder tumors.

Given the presence of the adverse events associated with use of neuromuscular blocking agents and the current lack of adverse events reported with the obturator block, we are interested in conducting an investigation comparing the two approaches in a prospective and randomized manner.

#### 5. Specific Aims:

The primary objective will be to compare the incidence of adductor spasm (also known as the obturator reflex) during transurethral resection of posterolateral bladder tumors under general anesthesia.

Secondary objectives will include assessments of leg weakness and fall risks, as measured using a handheld dynamometer and the timed up and go (TUG) test, respectively. Adverse events related to the anesthetic and surgical techniques will also be recorded.

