#### Planned statistical analyses

All analyses will be conducted in JMP Pro 12.0 (SAS Institute, Cary, NC). Categorical measures (e.g. block success) will be summarized as percentages (%). For continuous measures (e.g. TUG, dynamometer), normally distributed measures will be summarized as means and standard deviations, and non-normally distributed measures will be summarized as median with interquartile range. Differences in block success between groups will be examined with  $\chi^2$  tests. Differences in dynamometer measurements and TUG tests will be examined through t-tests, with transformation of outcomes as necessary to satisfy assumptions of the statistical test.  $P < 0.05$  will be considered statistically significant.

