#### Obturator block group

Standard of care: After the induction of general anesthesia, the block will be performed on the side of the posterolateral bladder tumor(s). If a patient has bilateral posterolateral bladder tumors, bilateral blocks will be performed. A time out procedure will be performed confirming the patient's identity, the proposed surgical procedure, and laterality of the tumor(s) and block procedure(s). The patient's inguinal region will be cleansed with Chlorohexidine prep solution. A 21ga Pajunk SonoPlex needle will be advanced under ultrasound guidance and 20-30mL of 2% mepivacaine will be injected using an interfascial approach. All nerve blocks will be performed by [name], who has expertise in ultrasound-guided regional anesthesia. Block time will be counted as the time from needle insertion until the completion of the injections. Any inadequate/failed blocks will be recorded. Unless clinically indicated, neuromuscular blocking agents will be avoided (with the exception of succinylcholine for tracheal intubation).

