#### Neuromuscular block group

Standard of care: After the induction of general anesthesia, rocuronium (a neuromuscular blocking agent) will be administered intravenously in 5-10mg increments

titrated to a goal of 2/4 twitches. An obturator block will not be performed unless adductor spasm persists despite the administration of additional rocuronium.

Research related procedure: The incidence of block- and procedure-related adverse events, including the obturator reflex, will be recorded. In addition to clinical observation, a Nerve Integrity Monitor (Medtronic) will be used to detect adductor spasm using continuous electromyography. Adhesive skin (non-needle) electrodes will be placed on the thigh to objectively detect and record instances of adductor spasm.

Standard of care: Unless contraindicated, all patients will be extubated and transported to the post anesthesia care unit (PACU). The patients will then be discharged home or to a hospital room (per the surgical service).

Research related procedure: One hour after arrival to PACU or when discharge criteria are met (whichever comes first), repeat dynamometer measurements and TUG tests will be performed. Patients will be called 24-48 hours post procedure to inquire about falls or evidence of nerve injury, as well as patient satisfaction.

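### Outside the reflex, failed blocks, falls and nerve injury, adverse events are recorded only if related to the technique, with no attribution rule or masking described, so a by-arm safety description can be biased

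*Combined protocol and SAP*

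**What the plan says.** Two sentences in the combined protocol and SAP set the general scope of adverse-event recording.

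- Section 5 (Specific Aims): "Adverse events related to the anesthetic and surgical techniques will also be recorded".
- Section 6, research procedures printed under Neuromuscular block group: "The incidence of block- and procedure-related adverse events, including the obturator reflex, will be recorded". I read this as applying to both arms, because the text that follows it concerns all patients.

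Both make relatedness a condition. Neither section provides for recording events regardless of cause.

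Some outcomes are collected without that condition:

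- Reflex: in addition to clinical observation, "a Nerve Integrity Monitor (Medtronic) will be used to detect adductor spasm using continuous electromyography".
- Failed blocks (Obturator block group): "Any inadequate/failed blocks will be recorded".
- Falls and nerve injury: "Patients will be called 24-48 hours post procedure to inquire about falls or evidence of nerve injury, as well as patient satisfaction".
- Leg strength and the timed up and go (TUG) test are measured before and after surgery.

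The documents give no definition of an adverse event, no relatedness criteria, no named assessor and no general collection window. They describe no masking. No sham injection is described either. In the comparator arm, "An obturator block will not be performed unless adductor spasm persists despite the administration of additional rocuronium".

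Planned statistical analyses names a chi-square test for block success and t-tests for dynamometer and TUG. It names no comparison of adverse events.

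**The concern.** Randomisation protects a comparison of all events by arm. It does not protect a comparison of events selected after treatment by a view of their cause, if that view can depend on the arm.

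Here it can. One arm receives a groin injection and the other titrated rocuronium, so the staff delivering the technique know which was used. The protocol also gives the arms different expected harms. Section 4 lists low oxygen, airway obstruction, weakness or fatigue, late extubation and aspiration for neuromuscular blockers. Section 7 lists nerve damage, paresthesia, hematoma and local-anesthetic complications for the nerve block. Section 4 then sets the known adverse events of the first technique against "the current lack of adverse events reported with the obturator block". A low oxygen reading in recovery fits the listed harms of one arm and not of the other.

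The exposed events are those outside the separately collected items: respiratory events, delayed extubation, general weakness, bleeding and perforation. Sections 3 and 4 treat these as important. Section 8 says that the relative safety of the two approaches is unknown and that the results may guide practice. An event left out for being unrelated is absent from the study data set, so no analysis of that data set can restore it.

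**Working it through.** **The plan's own figure.** The documents give no figure for adverse events. The only planned quantity used below is 30 patients per group (Sample size justification). That figure reproduces closely: 97% vs 69% block success needs 28 per arm, and a TUG difference of 7.4 with SD 10.0 needs 29 per arm (80% power, two-sided alpha 0.05). The point does not depend on it.

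**Which events pass through the relatedness condition.**

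| Event | Collected without the condition? |
|---|---|
| Obturator reflex | Yes: electromyography plus observation |
| Failed or inadequate block | Yes |
| Falls, nerve injury | Yes: asked at the 24-48 hour call |
| Leg strength, mobility | Yes: measured before and after surgery |
| Respiratory events, delayed extubation, general weakness, bleeding, perforation | No separate provision found |

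**Size of the distortion.** Let r be the true risk, equal in both arms, and let a1 and a2 be the probabilities that an event is called related in each arm.

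- Recorded risk = r × a1 and r × a2.
- False difference = r × (a1 − a2).
- False ratio = (r × a1)/(r × a2) = a1/a2, which does not depend on r.

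The values of r, a1 and a2 are assumptions; the documents give none. At 30 per arm, the chance of P<0.05 was found by enumerating all possible 2×2 tables.

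| r | a1 vs a2 | Recorded risk | Expected patients | False ratio | Chi-square | Fisher |
|---|---|---|---|---|---|---|
| 10% | 90% vs 70% | 9% vs 7% | 2.7 vs 2.1 | 1.29 | 5.8% | 0.8% |
| 10% | 90% vs 50% | 9% vs 5% | 2.7 vs 1.5 | 1.8 | 8.2% | 1.2% |
| 20% | 90% vs 70% | 18% vs 14% | 5.4 vs 4.2 | 1.29 | 7.2% | 2.9% |
| 20% | 90% vs 50% | 18% vs 10% | 5.4 vs 3.0 | 1.8 | 14.8% | 6.3% |
| 40% | 90% vs 70% | 36% vs 28% | 10.8 vs 8.4 | 1.29 | 9.8% | 6.0% |
| 40% | 90% vs 50% | 36% vs 20% | 10.8 vs 6.0 | 1.8 | 27.9% | 19.8% |

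For reference, 20% recorded in both arms gives 4.9% by chi-square and 2.2% by Fisher. A small gap does little: at r = 20%, 90% vs 80% gives about 5.5% by chi-square.

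Because the false ratio is a1/a2 whatever the true risk, related-only data cannot separate it from a real effect.

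**The case against.** A reader might infer that no adverse event is recorded in this trial unless judged related. The documents do not support that. The reflex, failed blocks, falls and nerve injury are all collected without an attribution step, and strength and mobility are measured. Numbness and unsteadiness are therefore largely covered.

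The condition can also be read broadly. Every patient has general anesthesia and a resection, so an event around surgery could count as related to the anesthetic or surgical technique in either arm. The protocol uses the word block for both arms, so the two sentences may be one idea in two wordings. No causality assessment is described, and related may mean little more than perioperative. This stands as a fair reading, but the text does not settle it, and recording only related events still needs someone to decide which events those are.

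No adverse-event test is planned, so the P<0.05 figures concern a test outside the plan. That stands. The assumed rates have no source in the documents, and narrow attribution gaps or Fisher's test make the effect small. That stands too.

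Section 3 concedes that the absence of reported complications may reflect underuse or under-reporting, so the investigators do not take the favorable history at face value. This weakens any suggestion that they would reproduce it, but it does not remove the mechanism.

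Finally, the documents do not say whether medical records could recover omitted events. The limit on correction therefore applies to the study data set, not to every possible source.

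**Conclusion.** The point holds for adverse events other than the reflex, failed blocks, falls and nerve injury. For those other events, recording is conditional on relatedness, in two wordings, with no attribution rule and no masking described. The absence of masking is read from silence; the documents do not state that the trial is open-label.

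The consequence is possible bias in a descriptive by-arm safety account. The planned tests of block success, strength and TUG are not affected. The false ratio equals the ratio of attribution rates: 1.29 to 1.8 under the two assumed gaps of 90% vs 70% and 90% vs 50%. The direction and real size are unknown. A reader might infer that the safety comparison will be biased, or that the bias is irreparable. The documents support only that it could be, and that the study data set alone could not correct it.

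This is a cheap improvement worth making before enrolment.

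**What to change.** Use one wording in section 5 and in the research procedures of section 6, for example: All adverse events from induction of anesthesia to the 24-48 hour call are recorded in both arms regardless of cause; relatedness is recorded as a separate item. Add to Planned statistical analyses that all adverse events are tabulated by arm as the main safety display, with related events as a secondary one.

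The cost is a wording change and one form field, with no extra visits or patients. Some background surgical events will be recorded and add noise. The change removes the attribution filter. It does not remove differences in how readily unmasked staff notice or report events, so that limitation should still be stated when safety is described.

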#### 6. Research Plan:

Veterans diagnosed with posterolateral bladder tumors will be invited to participate in the study. After obtaining written informed consent, the veteran will be randomized to receive an ultrasound-guided obturator block or a neuromuscular blocking agent after the induction of general anesthesia in an attempt to block the obturator reflex during surgery. Both techniques are commonly performed and accepted techniques for the prevention of the obturator reflex.

#### Inclusion criteria

1. Patients  $\geq$  18 years of age undergoing TURBT for unilateral or bilateral posterolateral bladder tumors
2. Ability to understand and provide informed consent

#### Exclusion criteria

1. Patient refusal or inability to provide informed consent
2. True allergy, not sensitivity, to any of the following substances:
  - a. Local anesthetics
  - b. Propofol
  - c. General anesthetic agents
3. Pregnancy
4. Severe hepatic impairment
5. Evidence of infection at or near the proposed needle insertion site
6. Any sensorimotor deficit of the lower extremity, whether acute or chronic, as determined by the PI
7. Inability to walk without assistance
8. Lower extremity joint replacement surgery in the preceding six months

#### Methods:

Research related procedures: Veterans (n=60) will be randomized to the obturator block or neuromuscular block arm upon enrollment, using randomized permuted blocks of six (GraphPad Software, Inc). The TUG test and dynamometer measurements will be obtained preoperatively and one hour postoperatively. Handheld dynamometers are commonly used to determine leg muscle strength and have been utilized in multiple recent nerve block studies and other clinical settings [7, 8, 15]. The TUG test requires the participant to stand from a seated position, walk ten feet, turn around, and return to a seated position. The test is free and available to all health care

providers (<http://www.cdc.gov/steady/index.html>). It is a sensitive and specific tool for evaluating fall risk with excellent intra- and interrater reliability [16]. It is easily performed, does not require specialized equipment or training, and correlates well with other balance and gait measures [17]. Times  $\geq 13.5$  seconds are associated with an increased risk of falls [16, 17].

Once a potential study candidate provides consent to participate in the study, s/he will undergo a baseline TUG test and dynamometer measurements.

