#### Sample size justification

The target sample size for the proposed study is  $n=60$  ( $n=30$  per group). Power calculations were performed assuming 80% power and  $\alpha=0.05$ . With  $n=60$ , our sample can detect a minimum 28% decrease in block success in the neuromuscular block group compared to the obturator block group, assuming a 97% success rate in the obturator block group. This sample size will also be able to detect a minimum group mean difference of 7.4 on the TUG ( $SD=10.0$ ).

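### Allocation at enrollment leaves an unstated gap before treatment in which patients can be lost, miss the single block operator, or be tested at baseline with the arm known

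*Combined protocol and SAP*

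**What the plan says.** - **Time of allocation.** The Methods section says "Veterans (n=60) will be randomized to the obturator block or neuromuscular block arm upon enrollment", in permuted blocks of six.
- **Time of treatment.** The Research Plan places consent first, after which "the veteran will be randomized to receive an ultrasound-guided obturator block or a neuromuscular blocking agent after the induction of general anesthesia". The two arm descriptions agree: "After the induction of general anesthesia, the block will be performed on the side of the posterolateral bladder tumor(s", and "After the induction of general anesthesia, rocuronium (a neuromuscular blocking agent) will be administered intravenously".
- **Who gives the block.** "All nerve blocks will be performed by [name], who has expertise in ultrasound-guided regional anesthesia". No deputy is mentioned.
- **Baseline tests.** The Methods section asks for TUG and dynamometer measurements after consent and before surgery. It does not say that they come before allocation.
- **Other routes to a relaxant or a block.** The neuromuscular arm may receive an obturator block if spasm persists despite further rocuronium. The obturator arm avoids neuromuscular blocking agents unless clinically indicated, with an exception for the agent used at intubation.
- **Not stated.** The plan gives no enrollment-to-surgery interval, no handling of cancelled cases or operator absence, no replacement rule or loss allowance, and no analysis set.

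**The concern.** Allocation starts the clock for the randomised comparison. Three things can go wrong between that moment and induction.

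1. **Loss.** Surgery is cancelled or the patient withdraws. The plan does not say whether such a patient counts among the 60.
2. **Non-delivery.** The patient comes to surgery when the operator is away. In the obturator arm the assigned treatment cannot then be given. In the neuromuscular arm it can, although the rescue block would be unavailable.
3. **Arm-aware baseline testing.** TUG and dynamometer results depend on effort. If they are taken after the arm is known, patient or tester may be influenced by it.

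With no analysis set defined, unblocked obturator patients could be dropped, moved to the other arm, or kept. Dropping or moving them departs from the randomised groups. Keeping them preserves the groups but draws the two success rates together.

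**Working it through.** **Inputs.** From the Sample size justification: 30 per arm, alpha 0.05, 80% power, 97% success in the obturator arm and a 28% decrease in the other. Read as an absolute decrease, this gives 97% − 28% = 69%. A two-sided test is assumed, since sidedness is not stated. Non-delivery and loss rates are also assumptions.

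**The plan's own figure.** With p̄ = (0.97 + 0.69)/2 = 0.83, the pooled normal formula gives

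n per arm = [1.96·√(2·0.83·0.17) + 0.8416·√(0.97·0.03 + 0.69·0.31)]² / 0.28² = (1.041 + 0.415)² / 0.0784 ≈ 27.04, rounded up to 28.

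Reading the decrease as relative (0.97 × 0.72 = 69.8%) gives 29 per arm. The stated 30 per arm is therefore reproduced to within two patients per arm, and there is no arithmetic error.

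**Power with full delivery.** Summing the binomial probabilities of all tables in which the uncorrected chi-square test rejects gives 89.9% at 30 per arm. The pooled normal approximation gives 84.1%.

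**Non-delivery.** Let a fraction c of the obturator arm go unblocked, succeed at 69%, and stay in the arm allocated. The arm's success rate becomes 0.97(1 − c) + 0.69c = 0.97 − 0.28c.

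| c | Obturator-arm success | Power, exact chi-square | Power, pooled normal |
|---|---|---|---|
| 0 | 97.0% | 89.9% | 84.1% |
| 5% | 95.6% | 83.3% | 78.5% |
| 10% (3 of 30) | 94.2% | 75.9% | 72.3% |
| 20% (6 of 30) | 91.4% | 60.6% | 58.9% |

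At 2 of 30 (c = 6.7%, success 95.1%) the exact figure is 81%. On the exact calculation, it takes about three unblocked patients to fall below the planned 80%.

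**Pure loss from the obturator arm.** Success rates stay at 97% and 69%; only the arm size changes.

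| Obturator vs neuromuscular | Power, exact chi-square | Power, pooled normal |
|---|---|---|
| 27 vs 30 | 86% | 81.6% |
| 24 vs 30 | 87% | 78.3% |

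The exact figures do not fall steadily because the test is discrete at these sizes. Loss alone costs the primary comparison little power; non-delivery costs much more.

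**The case against.** Randomising at enrollment is a legitimate choice, and the documents report no cancellation, operator absence or delay. Enrollment could take place on the day of surgery, and cases could be scheduled around the operator. This stands: the point is about an unguarded risk whose size is unknown.

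Several stronger readings are tempting, but the documents do not support them.

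- **Patients will be lost mainly from the obturator arm.** Cancellation has no stated reason to differ by arm. Only operator absence has a one-sided effect on the assigned treatment.
- **Operator absence touches the obturator arm alone.** The same operator performs all nerve blocks, so absence would also remove the rescue block in the neuromuscular arm.
- **Early allocation gains nothing, so the assignment could be opened after induction.** The obturator arm's restriction on neuromuscular blocking agents, with its intubation exception, means the team must know the arm when that restriction applies. Opening the assignment after induction could itself cause departures from the plan.
- **Dropping unblocked patients certainly biases the result.** Bias requires the loss to be related to spasm risk, and a day's operator absence has no evident link to it. Selective withdrawal cannot be excluded, since no concealment or blinding is described, but it is not shown.
- **The TUG figure must be revised as a consequence.** The detectable difference does grow with missing tests (7.36 at 30 per arm, 7.49 at 29, SD 10.0). Tests missed in recovery, however, come after induction whenever allocation occurs, so this is not a consequence of allocation timing.

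**Conclusion.** The concern holds as a design risk. Allocation precedes treatment by an unstated interval, delivery of the obturator arm's treatment rests on one operator, and baseline testing is not tied to a point before allocation. Its size depends wholly on an assumed non-delivery rate: power falls from 90% to 83%, 76% or 61% at 5%, 10% or 20%. This rests on the 97% and 69% success rates, a two-sided uncorrected chi-square test, 69% success in unblocked patients, and analysis as randomised. Pure loss of three obturator patients leaves about 86%. The effect of arm-aware baseline testing cannot be quantified from the documents. The case for change rests on the low cost of removing these risks, not on evidence that the losses will occur.

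**What to change.** - **Methods, time of allocation.** Replace allocation at enrollment with allocation on the day of surgery, shortly before induction. Open the assignment only after baseline TUG and strength are recorded and the block operator is confirmed available. Allocating before induction keeps the arm known when the obturator arm's restriction on neuromuscular blocking agents applies.
- **Sample size justification.** Count the 60 from that point.
- **Planned statistical analyses.** State that patients are analysed in the arm allocated, and report losses and non-delivery by arm.

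**Cost.** This is a wording amendment plus opening the assignment on the day of surgery; the target stays at 60. Patients whose surgery falls on a day without the operator are not randomised, so accrual may slow slightly.

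**Limit.** Later allocation does not address the intraoperative crossovers (the rescue block in one arm, a clinically indicated relaxant in the other). Their handling needs its own statement in the analysis plan.

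### Permuted blocks of one fixed, published size make some assignments predictable if the person who enrols has seen earlier arms; varied, undisclosed block sizes would reduce this at little cost

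*Combined protocol and SAP*

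**What the plan says.** The Methods section fixes the method, timing and block size in one sentence: veterans "will be randomized to the obturator block or neuromuscular block arm upon enrollment, using randomized permuted blocks of six". The sample size justification gives 30 per group, so each block holds three of each arm and ten blocks fill the trial.

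The treatments differ visibly: an ultrasound-guided needle block in one arm, titrated rocuronium in the other. The obturator block section says "All nerve blocks will be performed by" one named operator, who therefore knows each patient given a block. No section available to this review says who enrols patients, who generates or holds the list, or how assignments are concealed. No blinding or stratification is described. Two parts of the document ahead of section 3 were not available, so this absence is judged on the remaining text.

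On sequence, the Research Plan states "After obtaining written informed consent, the veteran will be randomized to receive an ultrasound-guided obturator block or a neuromuscular blocking agent", and Methods states "Once a potential study candidate provides consent to participate in the study, s/he will undergo a baseline TUG test and dynamometer measurements". Both steps follow consent. Neither sentence says which of the two comes first.

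**The concern.** When arms are visible and the block size is known, someone who counts patients can sometimes work out the next assignment before deciding whether to invite the next patient. If that knowledge influenced who was enrolled, the arms could differ at baseline.

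Eligible patients need not share one level of spasm risk. The Abstract says "Depending on the location of the tumor(s), electrocautery or surgical stimulation may result in stimulation of the obturator nerve", and the inclusion criteria admit patients "undergoing TURBT for unilateral or bilateral posterolateral bladder tumors". The exclusion that rests on judgement, "Any sensorimotor deficit of the lower extremity, whether acute or chronic, as determined by the PI", bears on the TUG and strength outcomes rather than on spasm.

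The analysis would not correct such an imbalance. The plan says "Differences in block success between groups will be examined with" a chi-square test, with t-tests for TUG and dynamometry, and names no covariate adjustment. Block success is not defined; presumably it means absence of adductor spasm.

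The open order of allocation and baseline testing is a smaller, separate matter. TUG and dynamometer results depend partly on effort and on the assessor, so knowledge of the arm could affect a baseline measured after allocation.

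**Working it through.** **Inputs.** Block size 6 (Methods). n = 60, 30 per group (Sample size justification). The plan gives no predictability figure to reproduce; its sample size fits ten full blocks: 10 × 6 = 60 and 10 × 3 = 30 per arm.

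**Assumptions.** There is one unstratified list. The observer knows the block size and counts patients. Treatment order equals allocation order. L is the number of most recent arms not yet seen when the next patient is considered.

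**Step 1: one block of six.** Suppose j assignments in the block have been seen, a of them in one arm. Then P(a) = C(3,a)·C(3,j−a)/C(6,j). A later assignment is certain if either arm already has three. Otherwise the best guess is the arm with more places left, right with probability max(3−a, 3−j+a)/(6−j).

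| j seen | P(certain) | Best guess right |
|---|---|---|
| 0 | 0 | 0.5 |
| 1 | 0 | 3/5 = 0.6 |
| 2 | 0 | 0.4×0.75 + 0.6×0.5 = 0.6 |
| 3 | 2/20 = 0.1 | 0.1×1 + 0.9×2/3 = 0.7 |
| 4 | 6/15 = 0.4 | 0.4×1 + 0.6×0.5 = 0.7 |
| 5 | 1 | 1 |

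**Step 2: average over the six positions.** The patient at position k is predicted from j = max(0, k−1−L).

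- L = 0: certain (0.1+0.4+1)/6 = 25.0%, or 15 of 60; best guess (0.5+0.6+0.6+0.7+0.7+1)/6 = 68.3%.
- L = 1: certain (0.1+0.4)/6 = 8.3%, or 5 of 60; best guess (0.5+0.5+0.6+0.6+0.7+0.7)/6 = 60.0%.
- L = 2: certain 0.1/6 = 1.7%, or 1 of 60; best guess (3×0.5+0.6+0.6+0.7)/6 = 56.7%.
- L = 3: certain 0%; best guess (4×0.5+0.6+0.6)/6 = 53.3%.

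At L = 0 a block has one, two or three certain assignments with probability 0.6, 0.3 and 0.1 (mean 1.5). Convolving ten blocks gives a mean of 15, with 2.5% and 97.5% quantiles of 11 and 19.

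**Step 3: alternatives at the same lag.** For one list of m + m, the L = 0 results have closed forms: certain 1/(m+1), and best guess [m + 2^(2m−1)/C(2m,m) − 0.5]/(2m). With m = 3 these return 1/4 = 25% and (3 + 1.6 − 0.5)/6 = 68.3%, as above. With m = 30 they give 1/31 = 3.2% and (30 + 4.87 − 0.5)/60 = 57.3%. The other 30 + 30 entries use the Step 1 formula with 30 in place of 3. Varied blocks (4, 6 and 8, equally likely) were simulated as lists of 60, with an observer who knows the set of sizes but not their order: 12,000 lists at L = 0, 5,000 at L = 1, 1,000 at L = 2 and 3,000 at L = 3.

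Certain / best guess right:

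| Latest arms unseen | Blocks of six | Varied 4/6/8 | One list 30 + 30 |
|---|---|---|---|
| 0 | 25.0% / 68.3% | 2.3% / 67.8% | 3.2% / 57.3% |
| 1 | 8.3% / 60.0% | 1.5% / 59.5% | 1.6% / 56.5% |
| 2 | 1.7% / 56.7% | 0.6% / 56.3% | 0.7% / 56.1% |
| 3 | 0% / 53.3% | 0.15% / 53.2% | 0.3% / 55.6% |

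**Step 4: effect of removing the lag.** Suppose two arms would be unseen under the current plan (1.7% / 56.7%), and a change in timing let every earlier arm be seen. Varied blocks would then give 2.3% / 67.8% and the single list 3.2% / 57.3%. Both are worse than the current plan on both measures.

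**Step 5: balance.** Varied blocks cut off at 60 are most uneven when a final block of eight stops after four assignments to one arm: 28 + 4 = 32 against 28. The 30 + 30 list ends even. By the hypergeometric distribution, its first 30 patients split no worse than 12:18 in 93.0% of lists and no worse than 11:19 in 98.1%.

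**The case against.** The strongest objection is that the premise is not in the documents. The 25% needs an enroller who has seen every earlier arm and tracks block starts. The protocol shows only that one operator performs the blocks; it does not say that this person enrols. A reader might infer that a quarter of assignments will be foreseen, or that enrolment will be biased. The documents support neither. This objection stands, and limits the point to a conditional risk.

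Second, every figure measures predictability, and none measures an effect on the spasm comparison. Entry is already limited to posterolateral tumors, and the documents give no spasm risk by location. This also stands.

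Third, varied blocks hardly lower the best guess, and selective enrolment needs only a good guess. That is correct: with all arms seen, the guess moves only from 68.3% to 67.8%. The gain is in certainty.

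Fourth, a reader might infer that opening the assignment on the day of surgery would be safer still. Step 4 shows that it could raise predictability above the current plan. It would also require the single block operator to be available until each assignment is known. That requirement should not be made.

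Finally, permuted blocks of six are a recognised design, and the reference to a potential candidate in Methods suggests that testing comes first. Both are fair. The first supports a low severity; the second leaves an ambiguity that one sentence would settle.

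**Conclusion.** The point holds as a conditional one. With a fixed, published block size and visible arms, an enroller who sees earlier assignments would be certain of between 0% and 25% of the next ones, depending on how many recent arms are unseen. The best guess would be right 53.3% to 68.3% of the time, against 50% by chance. These figures rest on a single unstratified list, known block starts and treatment in order of allocation. The documents do not state the lag, so no one scenario can be called the expected one.

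At the same lag, varied blocks or a single list lower both measures for zero, one or two unseen arms. The benefit is large only when arms are seen promptly, and by three unseen there is none. The documents do not establish selective enrolment, a baseline imbalance or a distorted primary result. Severity is low: a cheap improvement worth making.

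**What to change.** In Methods, replace the fixed blocks of six with randomly varied block sizes (for example 4, 6 and 8). State that the sizes are not disclosed to those who enrol, and that the list is held by existing staff who do not enrol. Holding the list privately is not enough by itself, because a known fixed size can still be worked out from visible arms.

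If the best guess with all arms seen is also to fall, use one concealed list of 30 + 30 instead. The price is looser balance during recruitment, which matters mainly if the trial stops early, and it does not improve on the current plan once three arms are unseen.

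In both the Research Plan and Methods, state that the assignment is opened only after consent, confirmed eligibility and the baseline TUG and dynamometer tests. Do not require opening on the day of surgery.

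The cost is a new list, a few sentences of protocol text and, with varied blocks, a possible final imbalance of at most 32:28. Sample size, treatments and planned tests are unchanged.
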